## **9.0 PROHIBITED AND RESTRICTED THERAPIES DURING THE STUDY**

### **9.1 Prohibited Therapies**

Patients in this study may not use vaccines for the treatment of cancer for up to one month before the first dose of ipilimumab. Concomitant systemic or local anti-cancer medications or treatments are prohibited while receiving study treatments.

Patients may not use any of the following therapies during the study:

- Any non-study anti-cancer agent (investigational or non-investigational);
- Any other investigational agents;
- Any other CTLA-4 or anti PD-1 or PD-L1 inhibitors or agonists;
- Immunosuppressive agents;
- Chronic systemic corticosteroids.

## 10.0 STUDY CALENDAR

Procedure	Screening (Day0-28)	Day 1 h	Day 2	Day 3	Day 4	Day 5	Day 22 h	Nivo q3 wks h	Ipi q6 wks h	Resp. Eval Day 70 ( $\pm 7$ days)	Nivo q3 wks h	Ipi q6 Wks h	6 month Follow up	F/U q 12 wks for 3 yrs +/7days
Informed Consent	X													
Inclusion/Exclusion Criteria	X													
Medical History	X													
Pregnancy Test	X a						X a	X a	X a		X a	X a		
Physical Examination	X				X		X	X	X		X	X	X	X
ECG (12 Lead)	X													
Vital Signs	X				X		X	X	X		X	X	X	X
Adverse Events Assessment	X				X		X	X	X		X	X	X	X
Serum Chemistry b	X	X			X		X	X	X		X	X	X	X
Hematology b	X	X			X		X	X	X		X	X	X	X
Urinalysis	X													
Hep B and Hep C panel	X													
Endocrine Panels c	X								X			X		X
Radiation Therapy d		X	X	X	X	X								
Ipilimumab Treatment f		X f					X f		X f			X f		X f
Nivolumab Treatment g							X g	X g			X g			X g
Bloods/T-cell Response e	X				X	X	X e	X e	X	X			X	
Stool Sample collection i	X					X				X			X	
Tumor biopsy j	X					X								
PET/CT Imaging or CT (chest abdomen and Pelvis)	X								X			X		Q 12 W
MRI Brain	X													
Efficacy assessment									X					X

**Protocol version 7.0 dated 31DEC2020**

- a. Only for pre-menopausal female patients
- b. SOC labs (COMP, CBC w/diff.).
- c. TSH, T3, T4 required at screening, every 9-12 weeks thereafter while on therapy with ipilimumab and Nivolumab and once a year unless warranted by symptoms or signs detected at follow up visits. May be requested by treating physician if clinically necessary.
- d. 6 Gy X5, daily
- e. Blood for immune monitoring studies will be collected at baseline, end of radiation therapy, at the time of the first three infusions of ipilimumab, at the time of the first three infusions of nivolumab, at response evaluation (day 70), and at 6 month follow up. See Appendix 2 for details.
- f. Ipilimumab infusion 1mg/kg q6 weeks. After Day 70 (+/- 7 days) response assessment, if patients have disease progression, patients will come off study. Patients who demonstrate partial, stable or complete response will continue to receive ipilimumab q6 weeks.
- g. Nivolumab infusion 360mg q 3 weeks. After Day 70 (+/- 7 days) response assessment, if patients have disease progression, patients will come off study. Patients who demonstrate partial, stable or complete response will continue to receive nivolumab q3 weeks.
- h. All Infusions will have a  $\pm$  3 day window
- i. Stool samples will be collected on Day 1, Day 22, and Day 70 and at 6 month follow up. See appendix 11 for details.
- j. Biopsies will be optional and will be obtained at baseline and at day 22.

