#### **Immune-Related Adverse Events (irAEs)**

Many of the adverse events considered related to ipilimumab may be immune in nature and presumably a consequence of the intrinsic biological activity of ipilimumab. An immune-related adverse event is defined as any adverse event associated with drug exposure and consistent with an immune-mediated event. Disease progression, infections and other etiologic causes are ruled out or deemed unlikely as contributing to the event. Supportive data, such as autoimmune serology tests or biopsies, are helpful but not necessary to deem an event an irAE. Events of unclear etiology which were plausibly "immune mediated" have been conservatively categorized as irAEs even if serologic or histopathology data are absent. These irAEs likely reflect a loss of tolerance to some self-antigens or an unchecked immune response to gut or skin flora. Some breakthrough of immunity may be inseparably linked to the clinical antitumor activity of ipilimumab.

Approximately 60% of subjects developed any grade irAEs which predominately involved the GI tract, endocrine glands, or skin. Based on data from the safety database, the number of subjects with serious irAEs was approximately 17%, including 10% for serious GI irAEs (diarrhea and/or colitis), 3% of serious endocrinopathy (primarily hypophysitis/hypopituitarism) and 2% of serious skin irAEs. Bowel perforation was reported in less than 1% of subjects. With few exceptions these irAEs were clinically manageable and reversible with supportive care or corticosteroids. In responding patients, addition of corticosteroids does not appear to have a temporal relationship to change in objective tumor response.

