### **Endocrinopathies**

Endocrinopathies have been observed following treatment with nivolumab. Most cases were of low or moderate grade. The events have typically been identified through either routine periodic monitoring of specific laboratories (eg, TSH) or as part of a work-up for associated symptoms (eg, fatigue). Events may occur within weeks of beginning treatment, but also have been noted to occur after many months (while still on treatment). More than 1 endocrine organ may be involved (eg, hypophysitis [pituitary inflammation] may need to be evaluated at the time adrenal insufficiency or thyroid disorder is suspected). Moderate- to high-grade cases were managed with hormone replacement therapy and, in some cases, with the addition of corticosteroids. In some cases, nivolumab treatment was held until adequate hormone replacement was provided.

Guidelines on the recommended management of endocrinopathies are provided in Appendix 6.

Early recognition and treatment of endocrinopathies are critical to its management. Subjects should be advised to seek medical evaluation if they notice new-onset fatigue, lightheadedness, or difficulty with vision or if baseline fatigue worsens. As fatigue is common in subjects with cancer, it is important that an evaluation/work-up distinguishes between non-drug-related causes (eg, progression of disease, anemia, concomitant medications, or depression) and a possible drug-related AE as the management can be quite different. The principal management of endocrinopathies is hormone replacement therapy. For subjects with moderate- or high-grade events, corticosteroids may also be used (Appendix 6). Consultation with a BMS medical monitor

should be sought for all moderate- and high-grade cases of Endocrinopathies.

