#### Hypothyroidism and Hyperthyroidism

OPDIVO can cause autoimmune thyroid disorders. Monitor thyroid function prior to and periodically during OPDIVO treatment. Administer hormone-replacement therapy for hypothyroidism. Initiate medical management for control of hyperthyroidism. There are no recommended dose adjustments of OPDIVO for hypothyroidism or hyperthyroidism.

In patients receiving OPDIVO as a single agent, hypothyroidism or thyroiditis resulting in hypothyroidism occurred in 9% (171/1994) of patients; the median time to onset was 2.9 months (range: 1 day to 16.6 months). Approximately 79% of patients with hypothyroidism received levothyroxine and 4% also required corticosteroids. Resolution occurred in 35% of patients.

Hyperthyroidism occurred in 2.7% (54/1994) of patients receiving OPDIVO as a single agent; the median time to onset was 1.5 months (range: 1 day to 14.2 months). Approximately 26% of patients with hyperthyroidism received methimazole, 9% received carbimazole, 4% received propylthiouracil, and 9% received corticosteroids. Resolution occurred in 76% of patients.

In patients receiving OPDIVO with ipilimumab, hypothyroidism or thyroiditis resulting in hypothyroidism occurred in 22% (89/407) of patients; the median time to onset was 2.1 months (range: 1 day to 10.1 months). Approximately 73% of patients with hypothyroidism or thyroiditis received levothyroxine. Resolution occurred in 45% of patients.

Hyperthyroidism occurred in 8% (34/407) of patients receiving OPDIVO with ipilimumab: the median time to onset was 23 days (range: 3 days to 3.7 months). Approximately 29% of patients with hyperthyroidism received methimazole and 24% received carbimazole. Resolution occurred in 94% of patients. Please refer to Appendix 6 for Endocrinopathy management algorithm.

Immune-mediated endocrinopathies, including life-threatening cases, can occur with YERVOY.

Monitor patients for clinical signs and symptoms of hypophysitis, adrenal insufficiency (including adrenal crisis), and hyper- or hypothyroidism. Patients may present with fatigue, headache, mental status changes, abdominal pain, unusual bowel habits, and hypotension, or nonspecific symptoms which may resemble other causes such as brain metastasis or underlying disease. Unless an alternate etiology has been identified, signs or symptoms of endocrinopathies should be considered immune-mediated.

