Monitor clinical chemistries, adrenocorticotrophic hormone (ACTH) level, and thyroid function tests at the start of treatment, before each dose, and as clinically indicated based on symptoms. In a limited number of patients, hypophysitis was diagnosed by imaging studies through enlargement of the pituitary gland.

Withhold YERVOY dosing in symptomatic patients and consider referral to an endocrinologist. Initiate systemic corticosteroids at a dose of 1 to 2 mg/kg/day of prednisone or equivalent, and initiate appropriate hormone replacement therapy

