## 6.0 STUDY THERAPY

Each patient will receive ipilimumab intravenously at 3 mg/kg on C1D1. Infusions will be given over 30minutes (not bolus or i.v. push).

Ipilimumab 3mg/kg will be administered on Day 1. On Day 22, ipilimumab (1mg/kg) will be given along with nivolumab (360mg). Subsequently, ipilimumab (1mg/kg) will be given every 6 weeks and nivolumab (360mg) will be given every 3 weeks.

Radiation will be delivered daily, Monday-Friday, for five consecutive days, at the Stich Radiation or DHK Radiation Oncology at Weill Comell Medicine-New York Presbyterian. A dose of 6 Gy x 5 days will be tested. All patients will be re-imaged by CT on Day 70 ( $\pm$ 7 days).

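### The study calendar requires no ACTH test before any ipilimumab dose and no thyroid test between screening and the Day 22 dose, although Section 1.3 calls for both before each dose

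*Combined protocol and SAP*

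**What the plan says.** Two parts of the protocol set endocrine monitoring, and they differ.

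- **Section 1.3, Hypothyroidism and Hyperthyroidism, ipilimumab text:** "Monitor clinical chemistries, adrenocorticotrophic hormone (ACTH) level, and thyroid function tests at the start of treatment, before each dose". The sentence goes on to add testing when symptoms indicate it. The next paragraph says "Withhold YERVOY dosing in symptomatic patients and consider referral to an endocrinologist".
- **Section 10.0, Study Calendar, footnote c:** "TSH, T3, T4 required at screening, every 9-12 weeks thereafter while on therapy with ipilimumab and Nivolumab". It then allows the treating physician to request the tests when clinically necessary. ACTH is not listed. Footnote b defines the other scheduled laboratory work as a metabolic panel and a blood count with differential.

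The dosing schedule is in Section 6.0. Ipilimumab 3 mg/kg is given on Day 1, and then "On Day 22, ipilimumab (1mg/kg) will be given along with nivolumab (360mg). Subsequently, ipilimumab (1mg/kg) will be given every 6 weeks".

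For nivolumab, Section 1.3 asks only for thyroid testing before and periodically during treatment. Under Endocrinopathies it describes events found through "routine periodic monitoring of specific laboratories (eg, TSH") or through work-up of symptoms. Footnote c is consistent with that. The mismatch is with the ipilimumab instruction only.

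**The concern.** The calendar is the schedule that sites work from. A site that meets its minimum exactly would give every ipilimumab dose without an ACTH result. It would also give the Day 22 dose, which starts dual blockade three weeks after the trial's highest ipilimumab dose, without a thyroid result since screening.

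The protocol itself treats this toxicity as serious. Section 1.3 states that "Immune-mediated endocrinopathies, including life-threatening cases, can occur with YERVOY" and warns that patients may present with "nonspecific symptoms which may resemble other causes such as brain metastasis or underlying disease". The trial admits patients with stable brain metastases (inclusion criterion 11), so that overlap is a practical one. In the ipilimumab safety database, serious immune-related events included "3% of serious endocrinopathy (primarily hypophysitis/hypopituitarism"), a pituitary disorder on which ACTH bears directly.

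What is at stake is timely recognition in patients with no symptoms or nonspecific ones. The response rate, the Simon design and the adverse-event analysis are not affected.

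**Working it through.** **Inputs**
- Screening window: up to 28 days before Day 1 (Section 10.0).
- Panel interval: 9–12 weeks, or 63–84 days (footnote c).
- Ipilimumab: Days 1 and 22, then every 42 days (Section 6.0), so Days 64, 106 and 148; the next is Day 190.
- Infusion window: ±3 days (footnote h).

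**ACTH**
- Section 1.3 implies a test at each of the 5 ipilimumab doses to Day 148.
- Neither footnote b nor footnote c lists ACTH, so the calendar requires 0.

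**Thyroid panel before Day 22**
- Earliest follow-up panel under footnote c: −28 + 63 = Day 35.
- Latest possible Day 22 dose: 22 + 3 = Day 25, which is still before Day 35.
- For a 9-week panel to fall due by Day 22, screening would have to be on Day 22 − 63 = −41, outside the 28-day window.
- As extracted, the Endocrine Panels row is blank at Day 22. It is marked at screening, at the two 6-weekly ipilimumab columns and at follow-up. Moving the first on-treatment mark one column either way puts it at the 3-weekly nivolumab column or at Day 70, and neither is Day 22.

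So the Day 22 thyroid gap holds under the footnote and under the row.

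**Thyroid panel before later doses (Days 64, 106, 148)**

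A dose counts as covered if a panel falls after the previous ipilimumab dose and on or before the dose in question. Two readings are possible.

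1. *Row as printed.* The 6-weekly ipilimumab columns each carry a panel, so Days 64, 106 and 148 are covered. Uncovered: Day 22 only, 1 of 4.
2. *Footnote c's interval alone.* The footnote does not say what the interval is counted from, so take every anchor from Day −28 to Day 1 (30 values) with every fixed interval from 63 to 84 days (22 values): 30 × 22 = 660 cases.

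| Uncovered doses | Cases |
|---|---|
| 22, 106 | 404 |
| 22, 64 | 110 |
| 22, 148 | 25 |
| 22, 64, 148 | 121 |

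Two doses are uncovered in 404 + 110 + 25 = 539 cases and three in 121. Day 22 is uncovered in all 660. Counting from Day 22 instead gives {22, 64} at 9 weeks and {22, 64, 148} at 10, 11 and 12 weeks, again 2 or 3 of 4.

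The readable text does not settle which reading is right. The ipilimumab row sits correctly at Day 22, which favours the printed marks. But the stool and biopsy marks are displaced from the Day 22 given in footnotes i and j. The endocrine row also has the same pattern as the imaging row, whose first on-treatment mark should be at Day 70. The case counts describe the footnote; they are not probabilities for patients.

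**The case against.** **The Section 1.3 text is background.** It is product-style wording in a summary of the drug programme, not a procedures section, and the nivolumab wording beside it agrees with footnote c. Section 6.0 also tells sites to follow the nivolumab brochure's management algorithms, which are aligned for combinations. This stands in part. Those algorithms concern handling of events, not routine testing. The sentence at issue is a direct monitoring instruction for a study drug, and no readable procedures text replaces it. Relaxing Section 1.3 to match footnote c would also remove the mismatch, so the choice between the two is partly clinical.

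**Symptomatic patients are already covered.** A reader might infer that a patient with fatigue at Day 22 would be dosed untested, because the Dose Delay Criteria exempt Grade 2 drug-related fatigue. The documents do not support that. Section 1.3 asks for testing when symptoms indicate, for a work-up of the causes of fatigue, and for endocrine signs to be treated as immune-mediated unless another cause is found. Footnote c lets the physician order tests, and the investigator may delay a dose on judgement. This objection stands. What remains is mainly the patient with no symptoms, or with symptoms too nonspecific to raise suspicion.

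**Results may not change dosing.** Grade 2 laboratory abnormalities need no delay, endocrinopathies controlled on physiologic replacement may resume, and Section 1.3 recommends no nivolumab dose adjustment for thyroid disorders. This stands as a limit on the benefit.

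**No demonstrated yield.** The 3% is a whole-database figure, not a rate three weeks after one dose. The documents give neither an onset time for ipilimumab hypophysitis nor a detection rate for ACTH screening. This also stands.

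**Conclusion.** The mismatch is real. ACTH is required at 0 of 5 ipilimumab doses to Day 148, and no thyroid test is required between screening and the Day 22 dose on any reading of the row or the footnote. These conclusions rest on the stated dosing days, the 28-day screening window and the footnotes as written.

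The further statement that 2 or 3 of the 4 later doses lack a thyroid panel follows from footnote c's interval alone. It should not be taken as established, because the row as printed leaves only Day 22 uncovered. The supportable range is 1 to 3 of 4.

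The number of patients who would be affected cannot be estimated from the documents. The expected gain is modest. The change is still worth making, because it carries out the protocol's own instruction on a toxicity it calls potentially life-threatening, at little cost.

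**What to change.** Amend the Endocrine Panels row and footnote c together to require TSH, T3, T4 and ACTH:

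- at baseline, with the screening panel allowed to serve for Day 1;
- on Day 22, before dosing;
- before each 6-weekly ipilimumab dose after that (Days 64, 106, 148 and onward).

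Keep the clause allowing further tests when clinically necessary. State the same analytes and times in Section 1.3.

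**Cost per patient to Day 148**
- ACTH: up to 5 tests. If all 48 patients stay on treatment, at most 48 × 5 = 240.
- Thyroid: 5 time points. The row as printed gives 4 (screening, Days 64, 106 and 148), so 5 − 4 = 1 extra panel. Footnote c alone gives 2 or 3 including screening, so 2 or 3 extra. The range is 1 to 3.
- Visits and draws: none added. Research blood is already taken at the first three ipilimumab infusions (footnote e). Every ipilimumab day from Day 22 is also a nivolumab day (22 + 21k), when Section 1.3 already calls for liver function tests.
- Some abnormal results will need follow-up.

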### Clinical Safety

Ipilimumab immunotherapy was FDA approved for the treatment of metastatic melanoma in March 2011. Ipilimumab has been administered to over 14,000 patients with different cancers with a dose range between 0.1 mg/kg and 20 mg/kg. Most experience with ipilimumab exists at the 3 mg/kg and 10 mg/kg dose levels. Patients who received ipilimumab at 3 mg/kg were treated in clinical trials conducted early in the development program and received either a single or multiple injections. Based on a Phase III randomized trial [45], ipilimumab was FDA approved for the treatment of metastatic melanoma in 2010 at the recommended dose of 3 mg/kg. This will be the dosage used in this trial.

Nivolumab monotherapy is approved for the treatment of unresectable or metastatic melanoma in multiple countries including Japan, the US, and the EU. Nivolumab is also approved for the treatment of metastatic NSCLC and renal cell carcinoma in the US.

Qualitative and quantitative information received as of 13-Apr-2016 has been consistent with the established safety profile as observed in clinical trials. No new safety concerns were identified based on the global post marketing reports.

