#### 4.0 STUDY DESIGN

A Simon's two-stage optimal design is chosen for this trial, thus 15 patients are required for stage 1. If 5 or more responses are seen then the trial will proceed to stage 2 and an additional 29 patients will be enrolled and treated. If a total of  $\geq 18$  objective responses are demonstrated the trial will achieve its main endpoint.

We expect to accrue up to a total of 48 patients, independently from their PD-L1 status.

**Objective 2.1:** To demonstrate safety of combining initial concurrent radiotherapy and Ipilimumab as an induction regimen to the combination of Ipi/Nivo in NSCLC

A Simon's two stage design study of combined RT and Ipi (RT-Ipi), followed by maintenance of ipi/nivo is proposed for patients with metastatic NSCLC. Bristol-Myers Squibb (BMS) will provide drug and study support (ipilimumab and nivolumab) to patients on study (see letter of commitment from BMS).

Eligibility criteria: Patients  $>18$  years of age with histologically proven metastatic NSCLC, at least two measurable sites of disease, adequate organ and bone marrow function, ECOG PS 0-1 or Karnofsky  $\geq 70\%$  and informed consent for participation. Systemic or local anti-cancer therapies must be completed at least 2 weeks before the start of treatment. Baseline PET/CT or CT (chest, abdomen, and pelvis) is required within 4 weeks from accrual.

Treatment: At study entry all measurable metastatic lesions identified clinically or at PET/CT are recorded. Choice of the metastasis to be biopsied before and after RT-Ipi is based on ease of access (lymph nodes and subcutaneous metastases are preferred) and the estimated lowest risk for complications associated with tissue acquisition. The treatment starts a week after biopsy (during this week patients undergo CT simulation for radiation therapy). A regimen of 6 Gy X 5 daily fractions will be delivered to the biopsied lesion. Patients will receive ipi 3 mg/kg i.v. over 30 minutes initiated within 24 hours of the first dose of RT to the biopsied measurable lesion, conformally or by IMRT, with image guidance, to maximally spare normal tissue. At day 22 patients are started on the ICB combination of nivolumab 360 mg q 3 weeks, ipi 1mg/kg q 6 weeks, administered until evidence of progression. Patients will be re-imaged by CT between days  $70 \pm 7$  days (Week 9) and evaluated for response.

[figure not shown]

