#### Dose calculations and administration

Describe timing of first dose from registration/randomization. For preparation and administration details to be included in your protocol [per institutional policies], please refer to the current Investigator Brochure, (Section 3.2) and/or pharmacy reference Appendix.

Day 1 ipilimumab will be given at a dosing of 3mg/kg. On day 22, nivolumab (360mg) and ipilimumab (1mg/kg) will be given together. Subsequently, ipilimumab (1mg/kg) will be given every 6 weeks and nivolumab (360mg) every 3 weeks. Both nivolumab and ipilimumab can be administered over 30 minutes.

When study drugs (ipilimumab or nivolumab) are to be administered on the same day, separate infusion bags and filters must be used for each infusion. It is recommended that nivolumab be administered first. The second infusion will always be ipilimumab, and will start approximately 30 minutes after completion of the nivolumab infusion.

Ipilimumab and nivolumab may be diluted in 0.9% Sodium Chloride Solution or 5% Dextrose solution.

The dosing calculations should be based on the body weight. If the subject's weight on the day of dosing differs by > 10% from the weight used to calculate the dose, the dose must be recalculated. All doses should be rounded up or to the nearest milligram per institutional standard.

Following the first doses of the combination of nivolumab and ipilimumab on day 22, nivolumab will be given every three weeks at a dose of 360 mg. Patients may be dosed no less than 12 days from the previous dose of drug; and dosed up to 3 days after the scheduled date if necessary.

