Treatment Planning: 3D-Conformal or IMRT treatment planning is allowed. This includes "field-in- field" beams as well as the use of dynamic multi-leaf collimator (MLC) derived using inverse planning or electronic compensator techniques. Field arrangements and technique should be chosen that satisfy the PTV dose coverage constraints and normal tissue dose constraints using Dose-Volume Histogram (DVH) analysis. By carefully selecting the gantry and table angle combinations that do not enter or exit through other organs of the body, the dose can be confined to the traditional treatment volumes. Non-coplanar beam arrangements are encouraged, but not required. Dose calculations with tissue inhomogeneity correction must be used. In view of the GI pattern of toxicity of ipilimumab, particular attention will be applied to limit exposure to the bowel. To mitigate this risk, normal tissue constraints of abdominal and pelvic organs will be employed from recommendations from AAPM Task Group 101 (66) and the H. Lee Moffitt Cancer Center experience using this fractionation schedule (67).

After completion of the first course of radiation + ipilimumab at a 3mg/kg dose on Day 1 (or within 24 hours of RT), the patient will start on day 22 the regimen of Nivolumab 360 mg q3 weeks and Ipilimumab 1mg/kg q6 weeks until evidence of progression.

Response assessment will be performed during Day 70 ( $\pm$  7 days) by imaging with PET/CT or CT (CAP).

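### The only ipilimumab dose in the study calendar, 1 mg/kg every 6 weeks (footnote f), is attached to the Day 1 cell, where the synopsis and Sections 4, 6 and 8.2 state 3 mg/kg

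*Combined protocol and SAP*

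**What the plan says.** The calendar in Section 10.0 has a row labelled "Ipilimumab Treatment f", where the f is a footnote mark. The mark is repeated in every filled cell of that row: Day 1, Day 22, both 6-weekly ipilimumab columns and the 12-weekly follow-up column. Footnote f gives the dose as "Ipilimumab infusion 1mg/kg q6 weeks". Its other two sentences deal with stopping or continuing after the Day 70 response assessment.

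The treatment text gives a different Day 1 dose:

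- Section 4.0: "Patients will receive ipi 3 mg/kg i.v. over 30 minutes initiated within 24 hours of the first dose of RT".
- Section 6.0, opening sentence: "Each patient will receive ipilimumab intravenously at 3 mg/kg on C1D1". The next paragraph has "Ipilimumab 3mg/kg will be administered on Day 1".
- Section 6.0, under dose calculations and administration: "Day 1 ipilimumab will be given at a dosing of 3mg/kg".
- Section 8.2: "radiation + ipilimumab at a 3mg/kg dose on Day 1".

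The synopsis schema and the sub-study in Section 22.0 also give 3 mg/kg with the first radiation dose. All of these places then move to 1 mg/kg every 6 weeks, starting on Day 22. Section 6.0 allows neither dose reductions nor escalations.

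**The concern.** The calendar and the treatment sections give different doses for the same infusion. That infusion, given with radiotherapy, is the induction that the trial adds to the ipilimumab and nivolumab combination. The primary objectives concern its safety and its effect on the response rate, and the safety criterion in Section 17.3 is tied to the ipilimumab-plus-radiation phase.

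The calendar is a working document for site staff. Section 11.0, despite its title, covers only completion or early withdrawal, so the calendar is the protocol's only visit-by-visit grid. The trial has more than one site, and the administrative section leaves sub-sites to manage the study locally. A reader who took the Day 1 dose from the grid would depart from Section 6.0, and no dose-modification rule covers that departure.

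**Working it through.** The plan has no calculated figure to reproduce here. The check is a comparison of passages plus simple arithmetic.

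**1. Which cells carry footnote f.** Counting columns in the calendar, the marks in the ipilimumab row fall under Day 1, Day 22, the two 6-weekly ipilimumab columns and the follow-up column. Two other rows confirm the alignment: the radiation marks fall on Days 1 to 5, and the first nivolumab mark falls on Day 22, both as Section 6.0 describes.

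**2. Whether the calendar gives a Day 1 dose elsewhere.** It does not. Footnotes a to e and g to j contain no ipilimumab dose, and the column headers give only the interval.

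**3. The statements side by side.**

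| Infusion | Footnote f | Synopsis, Sections 4, 6 and 8.2 |
|---|---|---|
| Day 1 | 1 mg/kg | 3 mg/kg |
| Day 22 | 1 mg/kg | 1 mg/kg |
| Then every 6 weeks | 1 mg/kg | 1 mg/kg |

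The dose conflict is confined to Day 1.

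**4. Size of the difference.** Ratio = 1 / 3 = 0.33. In milligrams, dose = mg/kg × weight. The weights below are assumptions:

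| Weight | Footnote f | Treatment sections |
|---|---|---|
| 50 kg | 1 × 50 = 50 mg | 3 × 50 = 150 mg |
| 70 kg | 1 × 70 = 70 mg | 3 × 70 = 210 mg |
| 90 kg | 1 × 90 = 90 mg | 3 × 90 = 270 mg |

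The infusion after Day 22 falls on Day 22 + 42 = Day 64. Cumulative dose is therefore:

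- through Day 22: 1 + 1 = 2 mg/kg by the footnote, 3 + 1 = 4 mg/kg by the treatment sections;
- through Day 64: 1 + 1 + 1 = 3 mg/kg against 3 + 1 + 1 = 5 mg/kg.

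**5. The interval.** Day 1 to Day 22 is 22 − 1 = 21 days, or 3 weeks. Footnote f says 6 weeks, or 42 days. The ±3-day infusion window in footnote h cannot close the gap: with both infusions at opposite ends of their windows, the interval is at most 21 + 3 + 3 = 27 days.

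**6. How the neighbouring footnotes work.** Footnote d gives the radiation dose and schedule, and footnote g gives the nivolumab dose and interval. Each agrees with the dose in Section 6.0 for the treatment it marks. Footnotes on treatment rows therefore do serve as dose statements in this calendar, and f is the one that disagrees with Section 6.0.

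**7. Effect on the design figures.** None. The two-stage calculation uses response rates of 31% and 51% and sample sizes of 15 and 44. Dose does not enter it.

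**The case against.** The strongest reply is that footnote f was written for the repeat infusions. It gives a 6-weekly interval, the rest of it concerns treatment after Day 70, and its interval cannot apply literally from Day 1 because the grid itself puts the next infusion 3 weeks later. The mark also sits in the 12-weekly follow-up column, so it may be a pointer for the whole row rather than an order for each cell. The treatment text agrees with itself in several places, including the subsection written for calculating doses.

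This is a plausible account of the intention, and it limits the point. It does not remove it. The footnote does not restrict itself to repeat infusions, and it is attached to the Day 1 cell. If it is read as excluding Day 1, the calendar gives no dose for that infusion.

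Two stronger readings should not be drawn.

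- A reader might infer a third regimen from the Clinical Safety text in Section 1.3, which says of ipilimumab "at the recommended dose of 3 mg/kg. This will be the dosage used in this trial". The documents do not support that. The sentence is background on the melanoma approval and sets no schedule, and Section 1.4 says that the 3 mg/kg dose is given once, with the initial radiotherapy.
- A reader might infer that the response rate and the safety result will describe a mixture of two regimens. That would require a site to dose from the footnote and disregard the synopsis and Sections 4, 6 and 8.2. Nothing in the documents indicates that any site has done so.

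**Conclusion.** Wrong as written. Footnote f and the treatment sections cannot both apply to the Day 1 infusion. The difference is 3-fold in dose, and the footnote's interval is twice the gap between the Day 1 and Day 22 cells that carry it. The fault lies in one calendar footnote, and the treatment sections are consistent with one another. Any effect on patients or on the analysis depends on a site taking its Day 1 dose from the calendar. The milligram figures depend on assumed body weights, but the ratio does not. This review does not say which dose is right, only that the passages must be reconciled. The correction is worth making because the infusion concerned is part of the induction under test and the calendar is the visit grid.

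**What to change.** Reconcile footnote f with the synopsis and Sections 4, 6 and 8.2. Give the Day 1 ipilimumab cell its own footnote, separate from the Day 22 and 6-weekly cells, so that the calendar and the treatment sections state one agreed dose and interval for each infusion. The sponsor decides the dose. The change is a wording edit that can go into the next amendment. It needs no extra patients or data and no change to the sample size, decision rule or error rates.
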